6.10 Study governance and oversight

6.10.1 Independent Data Monitoring Committee

An Independent Data Monitoring Committee (IDMC) will be convened and will meet approximately every 6 months for the first 2 years from the first patient randomised and approximately yearly thereafter. Further meetings for review of safety data may be convened at the discretion of IDMC. The IDMC will review safety assessments and make recommendations to continue, amend, or stop the study based on safety findings. Serious adverse events, adverse events, and other safety data will be reviewed, and individual and aggregated safety data will be evaluated by the IDMC. Furthermore, an IDMC will review the futility analysis outcomes and provide a recommendation for whether the study should continue. Full details of the IDMC procedures and processes can be found in the IDMC Charter.

7. INVESTIGATIONAL PRODUCT AND OTHER TREATMENTS

7.1 Identity of investigational product

AstraZeneca will supply AZD9291 as tablets for oral administration as a single daily dose of 80 mg.

Tablets will be packed in high-density polyethylene (HDPE) bottles with child-resistant closures. Bottles will be dispensed to patients in the AstraZeneca packing provided. The packaging includes bottles, caps, and a label. Bottle tampers should not be broken prior to dispensing the study drug to a patient.

Table 7 Identity of investigational products

Investigational product	Dosage form and strength
Test product	
AZD9291	40mg tablets 80mg tablets
Placebo	
AZD9291-matching placebo	NA

7.2 Dose and treatment regimens

Tablets can be taken whole with approximately 240 mL water, with or without regard to food.

Patients will be required to fast (water only) for at least 8 hours prior to the collection of a fasting glucose sample as per the Study Plan (See [Table 1](#)) and Section [5.2.1](#).

Study drug will be distributed as following:

- Randomisation – enough study drug for 1 month
- Week 4 visit – enough study drug for 2 months
- Week 12 visit onwards – enough study drug for 3 months

Individual bottles will be dispensed in accordance with the medication identification numbers provided by the IVRS/IWRS.

Patients should swallow 1 tablet once daily, commencing on Day 1 but no later than within 2 days from randomisation day. Tablets should be taken whole with water.

The initial dose of AZD9291 80 mg once daily can be reduced to 40 mg once daily.

On site visit days on which PK samples are scheduled, the dosing should be delayed until arrival at the site. Patients should not take their dose until instructed to do so by site personnel.

Doses should be taken approximately 24 hours apart at the same time point each day. Doses should not be missed. If a patient misses taking a scheduled dose, within a window of 12 hours, it is acceptable to take the dose. If it is more than 12 hours after the scheduled dose time, the missed dose should not be taken, and patients should be instructed to take the next dose at the next scheduled time. If a patient vomits after taking their study drug, they should not make up for this dose, but should take the next scheduled dose.

Any change from the dosing schedule, dose interruptions, or dose reductions should be recorded in the eCRF.

Additional information about AZD9291 may be found in the Investigator's Brochure.

7.3 Post study access to treatment

7.3.1 Patients receiving randomised study treatment

At the time of study analysis completion (final analysis per CSP v5.0), a number of patients may still be on study drug. These patients are to continue treatment until completion of the treatment duration, as long as, in the Investigator's opinion, they are gaining clinical benefit.

The treatment can be continued within the current study, and the following will apply:

- Assessment will revert to standard of care at particular site.
- There will be no further data collection except SAE reporting. Clinical Study Database would be closed.
- Paper form process will be used for SAE reporting. All SAEs, overdoses and pregnancies will be reported until 30 days after last dose.
- Study drug will be supplied to sites. Drug dispensation and reconciliation will be handled by site on each patient's visit.
- The study will be open until the last patient treated. Final Last Subject Last visit will be defined as the last patient's treatment discontinuation.

7.3.2 Patients receiving open-label osimertinib after recurrence

After the final OS analysis, AstraZeneca will continue to supply open-label osimertinib to patients receiving open-label osimertinib as long as, in the Investigator's opinion, the patient is gaining clinical benefit from active treatment. However, if osimertinib becomes available via commercial supply, where local regulations allow, patients should be switched from clinical study supplies to marketed product in those countries where it is approved for the disease under study.

7.3.3 Patients receiving open-label osimertinib post final OS analysis/during study extension for long-term OS analysis

After the final OS analysis, AstraZeneca will continue to supply open-label osimertinib to patients in both treatment arms as long as, in the Investigator's opinion, the patient is gaining clinical benefit from active treatment.

Patients are to be followed in accordance with the Medical SoC and as deemed appropriate by the investigators. It is recommended that investigators continue to observe ongoing patients at the frequency employed per protocol. Protocol dose modification and stopping criteria are to be followed while a patient is receiving osimertinib. A change in the dose/schedule of osimertinib should only occur for safety reasons, based on the Investigator's judgement, and should generally follow the approach for dose reduction and discontinuation as described in this protocol.

In the event that product development reaches a point where alternative product supply options become available, then these alternative product supply options will be discussed by AstraZeneca with the Investigator. AstraZeneca will work with the Investigator to transition the patient(s) to alternative supply, where possible.

In the event that a roll-over or safety extension study is available at the time of the final DCO and database closure, patient(s) currently receiving treatment with osimertinib may then be transitioned to such a study, and the current study would reach its end. The roll-over or extension study would ensure treatment continuation with visit assessments per its protocol, as applicable. Any patient who would be eligible to move to such a study would be given a new informed consent, as applicable.

7.4 Labelling

Labels will be prepared in accordance with Good Manufacturing Practice (GMP) and local regulatory guidelines. Label text will be translated into local language.

The label will include the Name of the Sponsor, Study Code, For Clinical Trial use only, and/or any other market specific requirements.

7.5 Storage

All study drugs should be kept in a secure place under appropriate storage conditions. The investigational product label on the bottles specifies the appropriate storage.

7.6 Compliance

The administration of all study drugs (including investigational products) should be recorded in the appropriate sections of the eCRF. Reasons for dose interruption, reduction, or omission will also be recorded in the eCRF. This information plus drug accountability for all study drugs at every visit will be used to assess compliance with the treatment.

7.7 Accountability

The study drug provided for this study will be used only as directed in the study protocol.

The study personnel will account for all study drug dispensed to and returned from the patient.

The study personnel at the investigational site will account for all study drugs received at the site, unused study drugs, and for appropriate destruction. Certificates of delivery and destruction should be signed.

7.8 Concomitant and other treatments

Information on any treatment within the 4 weeks prior to initiation of study drug and all concomitant treatments given up to 28 days after discontinuation of study treatment, with reasons for the treatment, will be recorded in the eCRF. Thereafter, only subsequent regimens of anti-cancer therapy will be recorded in eCRF.

Please see Section [3.9](#) for restricted concomitant medications during the study.

Other anti-cancer therapies, investigational agents, and radiotherapy should not be given while the patient is on study drug.

Pre-medication will be allowed after, but not before, the first dose of study drug. This includes management of diarrhoea, nausea, and vomiting, which should be administered as directed by the Investigator.

Use of concomitant medications that may cause QTc prolongation (e.g., antiemetic) should be avoided ([Appendix F](#)).

Supportive care and other medications that are considered necessary for the patient's well-being, may be given at the discretion of the Investigator.

7.8.1 Previous anti-cancer therapy

No prior anticancer therapy in preceding 5 years, including investigational therapy, with the exception of standard post-operative adjuvant chemotherapy for the treatment of NSCLC.

For patients who received post-operative adjuvant platinum-based chemotherapy, a minimum of 2 weeks must have elapsed but no more than 10 weeks from the last administered dose of chemotherapy to the date of randomisation.

If adjuvant platinum based chemotherapy is given, it is strongly recommended that this will be started within 8 weeks of surgery.

Patients who discontinue chemotherapy for toxicity prior to completion of all planned chemotherapy are eligible.

7.8.2 Other concomitant treatment

Other medication other than that described above, which is considered necessary for the subject's safety and wellbeing, may be given at the discretion of the Investigator and recorded in the appropriate sections of the Case Report Form.

8. STATISTICAL ANALYSES

8.1 Statistical considerations

A comprehensive Statistical Analysis Plan (SAP) will be prepared and finalised around the time of first patient in (FPI). All analyses will be performed by AstraZeneca or its representatives.

A single, primary analysis was planned for this study, with a further analysis performed only if there are meaningfully less than 70 DFS events in the Stage IB population. The primary endpoint of DFS and secondary endpoint of OS will be tested in the subset of patients with stage IIA-IIIA cancer as well as in the overall population, therefore in order to strongly control the type I error at 5% (2-sided), a hierarchical testing procedure will be employed across these endpoints.

[figure not shown]
The primary analysis of DFS was planned to be conducted when approximately 247 disease recurrence events have been observed in approximately 490 patients who are in Stage IIA-IIIA (i.e., non-IB). If the DFS result is statistically significant at the 5% (2-sided) alpha level, DFS in the overall population will then be assessed.

For the overall population analysis, it is estimated that there will be approximately 317 DFS events in approximately 700 patients, i.e., approximately 70 events in the Stage IB subgroup. If, however, there are meaningfully less than 70 DFS events (defined as 63 DFS events or less) in the Stage IB subgroup at the time of the primary analysis, additional follow up of patients may be performed and a further analysis of DFS may be conducted when there are approximately 70 DFS events in the Stage IB subgroup. Results from any additional analyses will be reported as an addendum to the CSR.

If the DFS results in both the non-Stage-IB population and the overall population are statistically significant, OS will then be assessed in the stage II/IIIA population, and then in the overall population if statistical significance is reached in the stage II/IIIA population.

An unplanned interim analysis for superiority was conducted by the IDMC and therefore efficacy analysis has been conducted prior to approximately 247 DFS events occurring in the stage II-IIIA population. Given this, the interim analysis has been taken into account to control the type I error rate at 5% (2-sided) and the multiple testing procedure has been revised. Further details regarding the multiple testing strategy is provided in the SAP and presented in the [Table 8](#) below.

Table 8 MTP diagram

An IDMC will review safety data on an ongoing basis and will conduct a futility analysis. Details of this analysis will be included in the statistical analysis plan and IDMC charter.

8.2 Sample size estimate

Approximately 700 patients will be randomised in a 1:1 ratio (AZD9291:Placebo) to this study. The primary endpoint of the study is DFS based on investigator assessment and will be assessed firstly in the stage II-IIIA population and then the overall population.

The primary analysis of DFS is planned to occur when approximately 247 disease recurrence events have been observed in approximately 490 patients who are in Stage IIa-IIIa (i.e., non-IB). If the true DFS hazard ratio (HR) for the comparison of AZD9291 versus placebo in this patient population is 0.70, 247 disease recurrence events will provide 80% power to demonstrate a statistically significant difference in DFS at a 5% 2-sided significance level (this could translate to an improvement in median DFS from 40 months to 57 months, assuming DFS is exponentially distributed). The minimum DFS HR that would be statistically significant ($p < 0.05$, 2 sided) is 0.78.

If the true DFS HR for the comparison of AZD9291 versus placebo in the overall population is 0.70, 317 disease recurrence events will provide ~90% power to demonstrate a statistically significant difference (this could translate to an improvement in median DFS from 46 months to 66 months, assuming DFS is exponentially distributed).

At the time of the primary analysis (when approximately 247 DFS have been observed), it is anticipated that approximately 195 OS events (28% maturity) will have occurred (assuming a median OS of 96 months for the placebo arm). If the true OS HR for the comparison of AZD9291 versus placebo is 0.66, 195 death events provides approximately 80% power to

demonstrate a statistically significant difference. With 195 death events and assuming a true OS HR of 0.85 there is approximately 90% chance of observing a HR < 1.02.

Assuming 28 months non-linear recruitment, the data cut-off for the primary analysis is estimated to occur approximately 68-70 months after first patient randomised.

It is estimated that 3200 patients will be screened in order to randomise 700 patients.

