1.3. Number of Patients

Approximately 700 patients will be randomised globally in a 1:1 ratio (AZD9291: placebo) to this study. The primary endpoint of the study is DFS based on investigator assessment. DFS will first be tested in the subset of patients with Stage IIA-III A cancer. If statistical significance is shown for DFS in the subset of patients with Stage IIA-III A cancer, then it will be tested for the overall population with the test mass split between first and second analyses.

The primary analysis of DFS will occur when approximately 247 disease recurrence events have been observed in approximately 490 patients who are in Stage IIA-III A (i.e. non-IB). If the true DFS hazard ratio (HR) for the comparison of AZD9291 versus placebo in this patient population is 0.70, 247 disease recurrence events will provide 80% power to demonstrate a statistically significant difference in DFS at a 5% two-sided significance level (translating to an improvement in median DFS from 40 months to 57 months, assuming DFS is exponentially distributed). The minimum DFS HR that would be statistically significant (i.e. $p < 0.05$, two-sided) is 0.78.

If the true DFS HR for the comparison of AZD9291 versus placebo in the overall population is 0.70, 314 disease recurrence events will provide approximately 90% power to demonstrate a statistically significant difference in DFS at a 4% two-sided significance level (translating to an improvement in median DFS from 46 months to 66 months, assuming DFS is exponentially distributed). The minimum DFS HR that would be statistically significant (i.e. $p < 0.04$, two-sided) is 0.79.

At the time of the primary analysis it is anticipated that approximately 195 OS events (28% maturity) will have occurred (assuming a median OS of 96 months for the placebo arm) in the overall population. If the true OS HR for the comparison of AZD9291 versus placebo is 0.66, 195 death events provide approximately 80% power to demonstrate a statistically significant difference at the 4% (two-sided) significance level. With 195 death events and assuming a true OS HR of 0.85 there is approximately 90% chance of observing an HR < 1.02 .

Assuming 28 months non-linear recruitment the data cut-off for the primary analysis is estimated to occur approximately 68-70 months after first patient randomised.

It is estimated that 3200 patients will be screened in order to randomise 700 patients.

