4.2.2. Multiple Testing Strategy

A single, primary analysis is planned for this study, with a further analysis performed only if there are significantly less than 70 DFS events (i.e. 63 DFS events or less) in the IB population at the time of the primary analysis. The primary endpoint of DFS and secondary endpoint of OS will be tested in the subset of patients with stage IIA-III A cancer as well as in the overall population. In order to describe the nature of the benefits of AZD9291 treatment, primary and secondary endpoints will be tested at a two-sided significance level of 5%. However, in order to strongly control the type I error at 5% two-sided level, a hierarchical testing procedure will also be employed across the primary endpoint and secondary endpoint of OS, intended for key label claims.

[figure not shown]
DFS in patients who are in Stage IIA-III A (i.e. non-IB) is tested first using the full test mass (full test mass = alpha).

DFS in the overall population will only be tested, with the test mass split between first and second analyses, if statistical significance is shown for DFS in patients who are Stage IIA-III A. OS (in both populations) will only be tested, with the test mass split between first and second analyses, if statistical significance is shown for DFS in the overall population.

Both DFS in the overall population and OS in both populations will be tested at the time of the primary analyses of DFS in patients who are Stage IIA-III A and may be tested again when at least 70 DFS events in the IB population have been observed (if there were significantly less than 70 DFS events at the primary analysis). Only a proportion of alpha will be spent at the first analyses for both endpoints to control for multiple testing.

The hierarchical testing procedure at the time of the primary analysis is shown in Figure 2. At the time of the primary analysis, DFS in patients who are in Stage IIA-III A is tested first using the full test mass of 5%. If this result is statistically significant, DFS in the overall population will be tested at 4%. If this result is statistically significant, OS in patients who are in Stage IIA-III A will be tested at 4%. If this result is statistically significant, OS in the overall population will be tested at 4%.

[figure not shown]
Figure 2 Hierarchical Testing Procedure at time of Primary Analysis

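### The only stated OS power (about 80% at HR 0.66 with 195 deaths) belongs to a superseded analysis; the OS test in force, at about 94 stage II-IIIA deaths, has no stated power or critical HR

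*Protocol*

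**What the plan says.** **OS power as printed.** Protocol 8.2 states "The primary analysis of DFS is planned to occur when approximately 247 disease recurrence events have been observed", expects about 195 deaths by then (28% maturity), and says "195 death events provides approximately 80% power to" show a difference at a true OS HR of 0.66. It names neither the alpha nor the population. It adds: "With 195 death events and assuming a true OS HR of 0.85 there is approximately 90% chance of observing a HR < 1.02". SAP 1.3 has the same plan in the future tense ("The primary analysis of DFS will occur when approximately 247 disease recurrence events have been observed"). It supplies the population ("approximately 195 OS events (28% maturity) will have occurred (assuming a median OS of 96 months for the placebo arm) in the overall population") and the alpha ("195 death events provide approximately 80% power to demonstrate a statistically significant difference at the 4% (two-sided) significance level").

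**OS test in force.** Protocol 8.1 puts the 247-event analysis in the past tense and says "the multiple testing procedure has been revised". The protocol synopsis, Protocol 8.7 and SAP 7 set the final OS analysis at about 94 deaths in stage II-IIIA. SAP 7 uses a Haybittle-Peto boundary, with 0.0002 two-sided at each interim and 5% overall. It leaves the exact final alpha to the observed information fraction and tests overall-population OS only if stage II/IIIA OS is significant.

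SAP 7 declares earlier text superseded only as regards alpha allocation. Its Tables 6 and 7 give critical HRs for DFS; it gives none for OS. Protocol Table 8 is a diagram that could not be seen here.

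**The concern.** Sections 8.2 and 1.3 are where a reader looks for OS power, and the only figure there describes an analysis that was overtaken. It uses a different population, about twice as many deaths and a different alpha from the test that decides the OS claim. Nothing in either section marks it as historical.

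A reader can therefore credit the OS test with 80% power at HR 0.66 and not see how large an effect it needs. Because of the gate, the chance of an overall-population OS claim cannot exceed the power of the stage II-IIIA test. SAP 4.2.2 describes this hierarchy as serving key label claims, so the operating characteristics of the gating OS test should be visible.

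**Working it through.** **Formulas** (log-rank, 1:1 allocation, *d* deaths, two-sided alpha):

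- Power = Φ(|ln HR|·√d/2 − z), with z the 1 − α/2 normal quantile
- Critical HR = exp(−2z/√d)
- P(observed HR < 1.02) = Φ(ln(1.02/true HR)·√d/2)

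**1. The printed figures** (SAP 1.3: d = 195, HR 0.66, 4%, z = 2.054).

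- Power = Φ(0.4155 × 6.982 − 2.054) = Φ(0.847) = 80.2%, as stated. The critical HR would have been 0.745.
- At 5% two-sided the power would be 82.7%, so the SAP's 4% is the matching level.
- Population: 195/700 = 27.9%, which agrees with the stated 28% maturity and confirms the overall population.
- Companion statement: Φ(ln(1.02/0.85) × 6.982) = Φ(1.273) = 89.8%, as stated.

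**2. Final alpha for the 94-death test.** The stage II-IIIA death counts at the interims are not given; Protocol 1.4 gives 29 deaths overall at IDMC7.

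- One 0.0002 look at information 0.15, 0.25 or 0.50 leaves 0.04986, 0.04990 or 0.04998. Simple subtraction leaves 0.0498.
- Two looks by simple subtraction leave 0.0496.
- Over 0.0496 to 0.05 the critical HR at 94 deaths moves only from 0.6670 to 0.6674. I use 0.0498 (z = 1.962).

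**3. The test in force** (d = 94, √94/2 = 4.848).

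- Critical HR = exp(−2 × 1.962/9.695) = 0.667.
- Power by assumed true stage II-IIIA HR:

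| True HR | Power |
|---|---|
| 0.50 | 91.9% |
| 0.56 | 80.2% |
| 0.66 | 52.1% |
| 0.70 | 40.8% |
| 0.85 | 12.0% |

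- The trigger is approximate. For 84 to 104 deaths (at 5%), power at HR 0.66 is 48% to 56% and the critical HR is 0.65 to 0.68.
- Counterpart of the companion statement: Φ(0.1823 × 4.848) = 81%, against 90% with 195 deaths.
- An observed HR of 0.70 with 94 deaths has a 95% CI of 0.70 × exp(±1.96 × 2/9.695) = 0.47 to 1.05.

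**4. Like-for-like comparison.** SAP 4.2.2 already tested stage IIA-IIIA OS first, at 4%. The number of stage II-IIIA deaths behind the 195 is not stated, so a share has to be assumed. At HR 0.66 and 4%:

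| Assumed share of 195 deaths | Deaths | Power | Critical HR |
|---|---|---|---|
| 70% | 137 | 64.7% | 0.704 |
| 247/317 (planned DFS split) | 152 | 69.4% | 0.717 |
| 156/196 (IDMC7 DFS split) | 155 | 70.3% | 0.719 |
| 85% | 165 | 73.1% | 0.726 |

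The old gating test therefore had about 65-73% power at HR 0.66, against 52% now.

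**5. Minor, SAP 1.3 only.** For DFS in the overall population, 314 events at HR 0.70 and 4% give Φ(0.3567 × 8.860 − 2.054) = 86.6%, not about 90%.

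**The case against.** The 80% is not miscalculated, and its sentence is tied to the 247-event DFS analysis under a heading about sample size. Elsewhere the protocol says in several places that this analysis was overtaken and gives the 94-death trigger. SAP 7 withdraws the 4% on which the SAP 1.3 power rests. Formal testing is complete (Protocol 8.8), and a finished test is read from its estimate, interval and p-value. The original plan did not state the gating test's power either. HR 0.66 was never stated for stage II-IIIA, the death split is assumed, and 94 is approximate.

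Much of this stands as qualification. The fault is un-updated text, not wrong arithmetic. The 52% depends on carrying HR 0.66 over to stage II-IIIA, and no test outcome is affected.

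It does not remove the point. The supersession in SAP 7 covers alpha allocation and leaves the 195 deaths, the HR and the 80% untouched. Nothing marks Protocol 8.2 as historical, although 8.1 was changed to the past tense. The deferred alpha is no obstacle, since the critical HR barely depends on it, and SAP 7 did print critical HRs for the revised DFS tests.

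**Conclusion.** The concern holds. The only OS power in the two documents' visible text belongs to a superseded overall-population analysis, and the OS test in force does not have that power. At about 94 stage II-IIIA deaths an observed HR above about 0.667 is not significant. Power is about 52% at HR 0.66 and reaches 80% only at about 0.56.

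The loss should not be put as 80% to 52%: on the same gating test it is about 65-73% to 52%. These figures assume proportional hazards, 1:1 allocation, a final alpha of 0.0496 to 0.05 and, for the comparison, that 70-85% of the 195 deaths were in stage II-IIIA. The absence of OS power and a critical HR is asserted for visible text only. The consequence is limited to how the OS result is read.

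**What to change.** In Protocol 8.2 and SAP 1.3:

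- Mark the 195-death sentences, including the one on HR < 1.02, as the original and superseded plan for the overall population (4% per SAP 1.3), with power calculated without regard to the stage II-IIIA gate. Put the 247-event analysis in the past tense.
- Add the properties of the revised test: final OS test at about 94 stage II-IIIA deaths; largest significant HR about 0.667, with the exact alpha set by the observed information fraction; power about 92%, 80%, 52% and 12% if the true stage II-IIIA HR is assumed to be 0.50, 0.56, 0.66 or 0.85; overall population tested only if this test succeeds. Since formal testing is complete, word this as the design of a test already set, not one to come.
- Minor: in SAP 1.3, mark the sentence on 314 DFS events at 4% as superseded and correct its power to about 87%.

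The cost is wording in two sections, and the stated OS power becomes less favourable. No patients, events or tests are added.
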